1.2 Secondary Objectives

Secondary objectives are to evaluate the efficacy of the self-administered hypnosis compared to self-administered sham white noise hypnosis for hot flash activity interference, sleep disturbance, anxiety and perception of benefit; with the expectation that there will be significant improvements among participants in the self-administered hypnosis group when compared with the self-administered sham white noise hypnosis group at 6 weeks. Further, we will evaluate the effects of self-administered hypnosis compared to the self-administered sham white noise hypnosis control at 12 weeks, for all secondary outcomes except perception of benefit.

Hypothesis 2.1

Compared to self-administered sham white noise hypnosis control, the self-administered hypnosis intervention will result in significant improvements in hot flash activity interference, sleep disturbance, and anxiety at 6 and 12 weeks, and perception of benefit at 6 weeks.

Additionally, mediators (perceived stress, cortisol, and heart rate variability (HRV) and moderators (hypnotizability and practice adherence) of hot flash reduction will be explored to address the following hypotheses:

Hypothesis 2.2

A decrease in perceived stress will be indicated in the self-administered hypnosis group due to the intervention, which will correspond and contribute to further decrease of the hot flash score at 6 and 12 weeks.

Hypothesis 2.3

Diurnal salivary cortisol will demonstrate better circadian rhythms (steeper slopes) in those with larger hot flash reductions and in the self-administered hypnosis group compared to participants in the self-administered sham white noise hypnosis at 6 weeks.

Hypothesis 2.4

Self-administration of hypnosis and greater hot flash reductions will result in higher resting and 24-hour parasympathetic activity, reflected as higher HRV at 6 weeks.

Hypothesis 2.5

Higher hypnotizability scores and better adherence rates will be associated with greater reductions in hot flash scores in the self-administered hypnosis group.

Hypothesis 2.6

Self-administered hypnosis will significantly decrease vasomotor symptoms (hot flash score of

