3. STUDY DESIGN

[figure not shown]
This study is designed as a randomized, two arm clinical trial to evaluate the efficacy of self-administered hypnosis for the treatment of hot flashes. The primary outcome will be the hot flash score,

which is determined from the frequency and severity of hot flashes obtained using the Hot Flash Daily Diary and will be determined at the 6-week data point.

Secondary endpoints will include: daily activity interference and overall quality of life measured by the Hot Flash Related Daily Interference Scale (HFRDIS), sleep disturbance measured by the Pittsburgh Sleep Quality Index (PSQI), and anxiety assessed by the PROMIS Emotional Distress - Anxiety Scale the Hot Flash Daily Diary at 6 and 12 weeks, and the Subject Global Impression of Change, at 6 weeks only.

It is expected that the hypnosis intervention will lead to decreased sympathetic nervous system (SNS) activity and increased parasympathetic tone. This shift in autonomic balance will have beneficial effects on

Figure 1: Conceptual Framework

hot flash score (frequency and severity-the primary outcome). Improvement in hot flashes will result in improvement in the secondary outcomes (activity interference, quality of life, sleep quality, and anxiety). Additionally, it is expected that perceived stress will decrease in the treatment group due to the intervention, which will correspond to further decrease of the hot flash score, but act as a mediator; and this will be measured with the Perceived Stress Scale. Because both autonomic arousal^[71] and psychological stress^[57] are believed to play a critical role in the initiation of hot flashes, we hypothesize that improvement in primary and secondary outcomes will be mediated by perceived stress and the autonomic response to hypnosis (**Figure 1**).

The comparison condition, called sham white noise hypnosis, is structured to account for non-specific effects of general time and attention, in addition to non-hypnotic audio-recordings to evaluate whether this self-administered hypnosis will reduce hot flashes more than an appropriate control group. This represents a rigorous RCT design.

There will be 232 participants who are postmenopausal or breast cancer survivors and wish to

avoid hormonal therapy to treat hot flashes.

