6. STUDY PROCEDURES

Schedule of Activities 6.1

Table 4: Schedule of Activities	Enrollmen	BL wk	Treatment and Follow-up in weeks						
	1 2 3		3	3 4 5		6 12			
Screening Checklist including PHQ-4	Х								
Informed Consent	X								
Demographic Questionnaire & Health History Intake		Х							
Aim 1 (primary outcome)									
Hot flash daily diary		D	D	D	D	D	D	D	D
Aim 2 (secondary outcomes)									
Hot Flash Related Daily Interference Scale		Х						Х	Х
PROMIS Emotional Distress- Anxiety Scale		Х						Х	Х
Pittsburgh Sleep Quality Index		Х						Х	Х
Global Impression of change								Х	
Aim 3 (mediators and moderators)									
Saliva collection for diurnal cortisol*		Х						Х	
HRV through Polar V800**		Х						Х	
[name] Hypnotizability Scale (only hypnosis group)		X***							
Frequency of home practice			D	D	D	D	D	D	D
Check In Phone Calls			Х	Х	Х	Х	Х	†	1

6.2 **Description of Evaluations**

The Schedule of Measures (**Table 4**) defines what is to be done at each week of the study period, which is approximately 13 weeks.

It is divided primarily by the type of evaluation (i.e.; Enrollment, Baseline, and Treatment & Follow-up). The Treatment & Follow-up period is further divided by study weeks.

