The PROMISTM Emotional Distress – Anxiety Scale contains 29 items that measure 5 domains of anxiety: 1) affective, 2) cognitive, 3) somatic, 4) behavioral, and 5) need for treatment. Items are scored on a scale from 1-5 with higher scores reflecting more severe anxiety. Like all PROMIS measures, the anxiety scale was developed through rigorous qualitative and quantitative assessment involving expert review, focus groups, and item response theory analysis, and it has shown excellent convergent and discriminate validity with other measures, with a Cronbach's alpha of .95.^[83, 84] This will be completed at baseline, 6 and 12 weeks.

Pittsburg Sleep Quality Index (PSQI)

The PSQI is a 19-item self-report inventory designed to measure sleep disturbance. The 19 items are grouped into 7 subscales: 1) sleep quality; 2) sleep efficiency; 3) daytime dysfunction; 4) sleep latency; 5) sleep disturbances; 6) sleep duration; and 7) use of sleep medication. These seven subscales are scored on a scale of 0-3 with higher scores indicating greater sleep pathology. Previous studies indicate that PSQI total scores are significantly correlated with measures of sleep onset latency, amount of time spent awake after initial sleep onset, and total sleep time as assessed by sleep diary and wrist actigraphy, [85] and alphas for the PSQI range from .70 to .80. [86] A cut point of 5 has been determined through evidence to differentiate sleep disturbance (≤5) from normal sleep. [87] This will be completed at baseline, 6 and 12 weeks.

Subject Global Impression of Change The Subject Global Impression of Change is a 7-point item in which the participant rates the change in hot flashes since beginning the study (ranging from "very much better," "moderately better," "a little better," "about the same," "a little worse," "moderately worse," to "very much worse"). It has been used extensively for determination of minimally clinically significant differences in numerous oncology clinical trials. [88, 89] Four additional investigator-developed questions will be included, of those four, two will ask about satisfaction . This will be completed only at 6 weeks. In addition, two questions about the use of audio recordings are included.

Diurnal Cortisol Rhythm

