6.2.3 Follow-up Visits

Week 1-6: Eligible participants will be randomly allocated to either a self-administered hypnosis group or a self-administered sham white noise hypnosis control group. Both groups will meet with a study research assistant two times (at baseline and at randomization/education visit) in person (or by telephone or video conference during COVID-19 restrictions) and further contact will be by phone through week 6 of the intervention period.

The interventions will be delivered through pre-recorded digital audio files, flash drives or CD's. For participants who prefer a flash drive or CDs, those will be provided. Additionally, if a participant prefers to use CDs, but does not have a CD player, one will be provided. Prepared self-management booklets will also be provided to each participant.

Participants in the self-administered hypnosis group and the self-administered sham white noise hypnosis group will use the self-management materials (booklets and audio recordings) for six weeks. A second kit to collect saliva and a Polar V800 HRV monitor will be mailed to participants during week five to be used for Week 6 data collection. At the end of Week 6, they will collect two days of saliva samples. HRV data will also be collected during the two days of saliva collection (as done during the baseline week) and both will be returned immediately following collection via a pre-posted mailer. However, if this collection was optional or unable to be completed due to COVID-19 restrictions, saliva samples and HRV data will not be collected at this time. At the end of Week 6, participants will return the completed hot-flash daily diaries, the self-hypnosis practice log, the questionnaire booklet with outcome measures of daily activity interference, quality of life, sleep disturbance, anxiety and stress in the provided pre-posted mailer. Due to COVID-19 restrictions, participants will also have the option of returning materials electronically (e.g., through DocuSign).

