6.2.4 Completion/Final Evaluation

Week 12: Before the start of week 12, participants will be telephoned to remind them of the 12 week data collection. The diary, log and questionnaires to be completed that week are included in the toolkit. At the end of week 12, participants will return the completed hot-flash diaries, self-hypnosis practice log, and complete questionnaire booklet that includes the measures of daily activity interference, quality of life, sleep disturbance, anxiety, stress and impression of change in the provided pre-posted mailer. Due to COVID-19 restrictions, participants will also have the option of returning materials electronically (e.g., through DocuSign).

Upon receipt of these measures, the Data Collection Quality Control Form: Study Completion will be completed, signed by the CRC, and countersigned by the PI.

Participants who complete the baseline and 6 week data collection will receive payment (gift card or check) in the amount of \$75 and if they complete the 12 week data collection, they will receive another payment (gift card or check) in the amount of \$50 to maximize retention for the longer data collection efforts.

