\pi_{1i} = \beta_{10} + \beta_{11}X_1 + r_{1i}
\beta_{00} = Grand mean hot flash score at baseline for control group
\beta_{01} = Expected difference in hot flash score at baseline between treatment and control groups
X_1 = Value of Treatment indicator (X); 0 = control, 1 = treatment
\beta_{10} = Average amount of change in hot flash score across time for control group
\beta_{11} = Difference in amount of change in hot flash score across time between treatment and control group
r_{0i} = Random error of intercept for participant i adjusted from group assignment [r_{0i} \sim N(0, \tau_{00})]
r_{1i} = Random error of amount of change for participant i adjusted from group assignment [)]
[r_{1i} \sim N(0, \tau_{10})]
Combined (Mixed) Model:
```

The effect of primary interest is the interaction between time and treatment, which is the $\beta_{11}X_1a_{ti}$ term.

 $Y_{ti} = \beta_{00} + \beta_{01}X_1 + \beta_{10}X_1 + \beta_{11}X_1a_{ti} + r_{1i}a_{ti} + r_{0i} + e_{ti}$

Objective #2

Secondary outcomes (activity interference from hot flashes, sleep disturbance, stress, and anxiety) will be entered separately as dependent variables into a similar type of longitudinal regression model described above. The primary difference in models is that for the secondary objectives, one set of models will be estimated using data collected at two points (i.e., baseline & week 6) and another set of models will be estimated using data collected at three time points (i.e., baseline, week 6, & week 12 [follow-up]).

Objective #3

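### The visit instructions place the Subject Global Impression of Change at week 12 and omit it at week 6, against the rest of the protocol, and Objective #2 gives no analysis that fits it

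*Combined protocol and SAP*

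**What the plan says.** The protocol fixes perception of benefit, measured by the Subject Global Impression of Change, at week 6 in several places.

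- Hypothesis 2.1 in section 1.2, repeated in 9.2, predicts improvement in activity interference, "sleep disturbance, and anxiety at 6 and 12 weeks, and perception of benefit at 6 weeks". The paragraph before it in 1.2 limits the 12-week evaluation: it is "for all secondary outcomes except perception of benefit".
- Section 3 ends its list of secondary endpoints with "and the Subject Global Impression of Change, at 6 weeks only".
- Section 6.2.2.2, describing the instrument and its investigator-written extra questions, says "This will be completed only at 6 weeks".
- Table 4 has a row for "Global Impression of change" with one mark. The other three secondary scales have three marks each.

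The two sections that describe what participants send back differ. At the end of week 6 (6.2.3 Follow-up Visits), they return the diaries, the practice log and "the questionnaire booklet with outcome measures of daily activity interference, quality of life, sleep disturbance, anxiety and stress in the provided pre-posted mailer". At week 12 (6.2.4), the same constructs appear with one addition: "sleep disturbance, anxiety, stress and impression of change in the provided pre-posted mailer".

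For the analysis, Objective #2 in 9.7 states: "Secondary outcomes (activity interference from hot flashes, sleep disturbance, stress, and anxiety) will be entered separately as dependent variables". The models there use baseline and week 6, or baseline, week 6 and week 12.

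**The concern.** The two return lists run parallel, and the only construct that differs between them is the one the rest of the protocol assigns to the other week. Anyone who assembles or checks booklets from 6.2.3 and 6.2.4 would leave the item out where the hypothesis needs it and include it where no hypothesis uses it. Section 6.2.4 also ties the study-completion form to receipt of the week-12 measures it lists, so a literal check would look for the item at that time.

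A week-12 answer is not a substitute. The item asks how hot flashes have changed since the woman began the study, so a week-12 rating covers a further 12 − 6 = 6 weeks after the structured programme ends and answers a different question from Hypothesis 2.1.

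Even with the item collected at week 6, section 9.7 does not say how the arms will be compared on it. A seven-category rating can be analysed as a mean score, as a responder proportion at some cut-point, or as an ordered scale. Leaving this open allows the choice to be made after the data are seen.

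**Working it through.** The point rests on text and not on a figure in the plan, so the check sets the places side by side.

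| Place | Week 6 | Week 12 |
|---|---|---|
| 1.2 and 9.2, Hypothesis 2.1 | yes | no |
| 3, Study Design | yes (only) | no |
| 6.2.2.2, instrument description | yes (only) | no |
| 6.1, Table 4 | one mark, consistent with week 6 | no second mark |
| 6.2.3 Follow-up Visits | not listed | – |
| 6.2.4 Completion/Final Evaluation | – | listed |

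The column alignment of Table 4 is broken in the text available for this review. The number of marks in the row is clear; their position should be confirmed on the original page.

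**Can the two sides be read as compatible?** The silence of 6.2.3 could be passed over as a loose summary. The entry in 6.2.4 cannot, because it adds a week-12 collection that sections 3 and 6.2.2.2 rule out. At least one passage is wrong as written.

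**Does any other section settle it?** Section 10.1 says the questionnaire booklets compile the outcome questionnaires for weeks 6 and 12, but does not itemise them by week. Its general statement on self-report measures gives baseline, week 6 and week 12 for all of them except the diary. That cannot be literally right for a rating of change, which has no baseline. So 10.1 does not resolve the contradiction.

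**Can the Objective #2 model be applied?** Objective #2 uses a model similar to that of Objective #1. Substituting the level-2 equations into level 1 gives, apart from random terms,

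E(Y) = β₀₀ + β₀₁X + β₁₀a + β₁₁Xa,

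where X is treatment (0 or 1) and a is time. The effect of interest is β₁₁, the difference in slope. The impression item has one planned value per woman, so a takes a single value. The expected values are then

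- control: β₀₀ + β₁₀a
- treatment: β₀₀ + β₀₁ + β₁₀a + β₁₁a
- difference: β₀₁ + β₁₁a

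Two arm means cannot identify four coefficients. Only the sum β₀₁ + β₁₁a can be estimated, so the slope difference is not estimable. The random intercept, random slope and residual cannot be separated either, with one observation each.

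**Is another analysis stated?** Section 9.2 promises intention-to-treat analysis of each secondary measure, and 9.7 adds multiple imputation. Neither names a test, model or scale for this item.

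**What is affected?** Hypothesis 2.1 has four outcomes: interference, sleep disturbance, anxiety and perception of benefit. One of the four is affected. The sample size (190, or 232 with attrition) is based on the hot flash score and does not change.

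**The case against.** The strongest reply is that the intended time is obvious. Section 6.2 says the schedule in Table 4 defines what is done each week, and the objectives, design section and instrument description agree with it. The lists in 6.2.3 and 6.2.4 are narrative summaries. They name quality of life, for example, which has no separate instrument and comes from the interference scale. Under 10.2 one coordinating centre approves the documents and supplies forms for both sites, and section 3 provides administrative calls to chase returns. On this view a phrase has slipped under the wrong week, and an analyst would choose a sensible ordinal method anyway.

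Much of this stands, and it limits the consequence. A reader might infer that the week-6 rating will be lost for all women, or for one site's share of them. The documents do not support that: nothing says booklets are built from 6.2.3 and 6.2.4, and nothing suggests the sites build them separately. A reader might also infer that a missed item could never be recovered. The administrative calls leave room for follow-up, though a late answer would be imperfect. Nor is this the only measure of whether women feel better, since the diary severity ratings and the other scales are also self-reported. It is the only global rating of change.

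Finally, the presence of stress in Objective #2 might look like a mediator listed by mistake. It should stay. The Perceived Stress Scale is described in 9.6.2 among the secondary outcomes, Hypothesis 2.2 predicts a decrease in the hypnosis group, and Objective #3 already covers mediation. Removing stress would delete the stated longitudinal between-arm model for it.

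The reply does not remove the contradiction. An instruction that needs four other places to override it should be corrected.

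**Conclusion.** The contradiction is real: the return lists in 6.2.3 Follow-up Visits and 6.2.4 conflict with Hypothesis 2.1, section 3, section 6.2.2.2 and, as far as its single mark shows, Table 4. It puts at risk the timing of one of four Hypothesis 2.1 outcomes. No share of missing data can be derived from the documents, and none is claimed. The conclusion assumes that week 6 is the intended time, which the weight of the text supports.

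The analysis gap is secondary. It is certain that the Objective #2 model cannot be fitted to this item, but on its own this is mostly missing detail. The point merits correction and does not affect the primary endpoint.

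**What to change.** 1. In 6.2.3 Follow-up Visits, add the Subject Global Impression of Change and its added questions to the week-6 booklet.
2. In 6.2.4, delete impression of change from the week-12 list.
3. Check the printed and electronic booklets against Table 4. If any have been issued with the item in the week-12 booklet, record which participants received them.
4. In Objective #2 of 9.7, add perception of benefit as a between-arm comparison of the seven ordered categories at week 6. Name one method in advance, either a proportional-odds model or a Wilcoxon rank-sum test, and say how missing answers are handled. Leave stress where it is.

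The cost is wording in two visit sections, one or two sentences in 9.7 and a booklet check. There are no new data and no added burden for participants, and the sample size is unchanged.

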7. SAFETY ASSESSMENTS

Study progress and safety will be reviewed monthly (and more frequently if needed). Progress reports, including patient recruitment, retention/attrition, and AEs will be provided to the DSMB every six months. A report will be compiled and will include a list and summary of AEs. In addition, this report willaddress (1) whether AE rates are consistent with pre-study assumptions; (2) reason for dropouts from the study; (3) whether all participants met entry criteria; (4) whether continuation of the study is justified on the basis that additional data are needed to accomplish the stated aims of the study; and (5) conditions whereby the study might be terminated prematurely. The report will be provided to the Board members and will be forwarded to the IRB; institution-based DSMBs as required by the institution; and NCCIH along with a letter of recommendation from the Board Chair. The IRB, NCCIH, and other applicable recipients will review progress of this study on an annual basis

7.1 Specification of Safety Parameters

We are excluding women around mental health diagnoses and screening with the PHQ-4 that would make hypnosis a potentially unsafe intervention.

7.2 Methods and Timing for Assessing, Recording, and Analyzing Safety Parameters

Expected risks are minimal. However, plans to address potential risks to the participant are as follows:

- Anxiety: Severe or acute anxiety or agitation will be evaluated pre-study during the history intake, as well as assessed through phone follow ups. The main risk related to this study is increased anxiety from a sense of worry about whether one is performing the assigned treatment arm correctly. Negative side effects have not been realized in any of the previous studies [name] have completed with hypnosis, including the structured control and white noise arms. [38, 41] In fact, in all of those studies, participants in both arms generally improved in most aspects of health-related quality of life such as anxiety, agitation and feelings of well-being. Any evaluation of developing issues with acute anxiety or distress, as evaluated by research assistants who will be contacting participants throughout the study, will be immediately brought to the attention of the PI's at Baylor and the University of Michigan. At the University of Michigan, a referral will be made to psychology or psychiatry. There is also an on-call psychiatrist available Monday through Friday from 8 a.m. to 5 p.m. to assist with crisis situations. After hours, an on-call consultant can be reached by calling the clinic operator and arrangements can then be made to have the patient seen in the Emergency Room if necessary by the on-call psychiatrist. At Baylor University, a referral will be made to the Baylor Psychology Clinic which is open Monday through Friday from 8 a.m. to 7:30 p.m. After hours, participants will be referred to the Emergency Room at Baylor Scott and White Health Center. Research assistant staff are trained in all study procedures, and work directly under the supervision of [name], PhD, and [name], RN, PhD, FAAN. Measures will be taken to ensure each woman understands her right to withdraw from the study at any time for any reason. If the research assistant assesses, at any time, that study participation is causing increased distress or an undue burden on a participant, they will address this issue and again assure the woman of her right to withdraw.
- Emotional distress: While there does exist the risk of emotional distress, the risk is rare with the type of hypnotic induction used in this study. If participants score 9 or over on the PHQ-4, they will be referred to their provider immediately for care. Participants will be advised during the consent process that this referral may be required. Participants will be advised of this as a risk, and any participant who experiences emotional distress will be given the opportunity to discuss her feelings with the PI, and if needed, further referrals will be made.

- HRV Recording device: The Polar V800, a mobile HRV recording device is a non-significant risk device if the protocol's exclusionary criteria are adhered to. Wearing the device can be a minor inconvenience, comparable to that of a standard wrist watch. The device poses no risk of electric shock. There are no known potential toxicities, however there could be skin irritation caused by the band that goes around the wrist and chest.
- Loss of confidentiality: there is a small risk that confidential information could be seen by someone not directly involved in the study activities. The investigators have developed critical processes to minimize this risk including research coding that does not include PHI, locked files, and encrypted and firewall protected databases.

These risks are considered to be minimal and are described in the protocol and consent form.

Steps will be taken to minimize any potential risks associated with study participation. Participation in this research study is strictly voluntary. The participant may opt to withdraw consent at any time for any reason. The investigator will notify the participant of any new information related to risk, toxicity, or efficacy that could influence the decision by the participant or investigator to continue study therapy.

